10.8 Data and Safety Monitoring Plan

The NIAID Intramural DSMB includes independent experts that do not have direct involvement in the conduct of the study and have no significant conflicts of interests as defined by NIAID policy. The Board reviewed the study prior to initiation and will review the study yearly thereafter, unless otherwise recommended by the Board. Given the seasonal nature of influenza (generally November through April) the interim reviews will occur after each influenza season. The Board may convene additional reviews as necessary. The Board will review the study data to evaluate the safety, efficacy, study progress, and conduct of the study. All SAEs, all UPs, and all IND Safety Reports will be reported to the DSMB by the CSO. The DSMB will be notified of any cases of intentional or unintentional unblinding as soon as possible.

As a guideline for monitoring results comparing randomized treatments for the primary endpoint, as it is unlikely that this trial will be replicated, a high level of evidence concerning any favorable effect of high-titer versus low-titer anti-influenza plasma is considered desirable before considering early termination of the study. For this reason, the Peto-Haybittle stopping guideline will be used; this requires a nominal p-value of < 0.001 at an interim analysis in order for termination to be considered. Such a level of evidence would also facilitate more precise comparison of effects in patient subgroups and for secondary endpoints. Although application of this guideline is focused on the primary endpoint, if a similar level of evidence is achieved first in comparing mortality rates between randomized arms, then termination of the study might also be considered.

If accrual is slower than anticipated such that the study is not fully enrolled within three years, then a futility analysis may be conducted at that time (i.e. after about three years of enrollment). The DSMB may recommend termination or modification of the study if it appears unlikely that continuation of the study will demonstrate a benefit of high titer plasma on the primary endpoint. Conditional power provides a measure for evaluating futility: specifically, conditional on the results observed at an interim analysis, it is the power of the study to show a significant benefit of high titer plasma assuming an underlying true difference between the randomized arms (that will determine what future data might be observed). Conditional power will be evaluated both (a) under the assumption that high titer plasma truly affects the primary endpoint by the amount assumed in designing the study (providing 90% power—see Section 1.2); and (b) for a range of true effects that appear plausible based on the observed rates at the time of the interim analysis.

Consideration of futility with respect to conditional power requires consideration by the DSMB of the broad array of information available at an interim analysis and of the value of continuing the study even if conditional power for the primary endpoint might be low. For example, this might be because of effects being observed on mortality or other secondary endpoints or because continuing the study might be valuable in showing definitively a lack of an effect of high titer versus low titer plasma. As guidance,

however, if the conditional power to show an effect of high versus low titer plasma if the study continued to its planned sample size is lower than 20% under a range of plausible situations covered by (a) and/or (b) above, then the DSMB might recommend study termination.

Each site PI will submit the written DSMB summary reports with recommendations to their IRB(s).

10.9 Pausing Rules

The population enrolled in this study is a critically ill population, and based on the IRC002 data will likely have many SAEs due to the underlying illness. The medical monitor's review of the safety data is most likely to detect signals suggesting subject safety is compromised. However, below are absolute criteria for which the study will be paused to further enrollment until assessed by the sponsor medical monitor:

- Two or more of the same unexpected SAE (unexpected AE in terms of previously described risks in the Investigator's Brochure) that are probably or definitively attributed to the study plasma.
- Four or more of the same SAE that can be possibly, probably, or definitively attributed to the study drug.

The sponsor medical monitor will ultimately make the decision to either resume the study, ask for formal DSMB review, or stop the study.

11 STUDY MONITORING

As per ICH-GCP 5.18 and FDA 21 CFR 312.50, clinical protocols are required to be adequately monitored by the study sponsor. This study monitoring will be conducted according to the "NIAID Intramural Clinical Monitoring Guidelines." Monitors under contract to the NIAID will visit the clinical research site to monitor all aspects of the study in accordance with the appropriate regulations. The objectives of a monitoring visit will be:

- 1) to verify the existence of signed informed consent documents and documentation of the informed consent process for each monitored subject;
- 2) to verify the prompt and accurate recording of all monitored data points, and prompt reporting of all SAEs;
- 3) to compare abstracted information with individual subjects' records and source documents (subjects' charts, laboratory analyses and test results, physicians' progress notes, nurses' notes, and any other relevant original subject information); and
- 4) to help ensure investigators are in compliance with the protocol.

The monitors also will inspect the clinical site regulatory files to ensure that regulatory requirements (Office for Human Research Protections-OHRP), FDA, and applicable guidelines (ICH-GCP) are being followed. During the monitoring visits, the investigator (and/or designee) and other study personnel will be available to discuss the study progress and monitoring visit.

The site investigator (and/or designee) will make study documents (e.g., consent forms) and pertinent hospital or clinical records readily available for inspection by the local IRB, the U.S. FDA, the site monitors, and the NIAID staff for confirmation of the study data.

12 STATISTICAL CONSIDERATIONS

12.1 General Considerations

This is a randomized, double-blind study comparing high-titer versus low-titer anti-influenza immune plasma for the treatment of subjects hospitalized with severe influenza A infection. The primary analysis population for the evaluation of both efficacy and safety outcomes will include all subjects who have the

study plasma infusion started. This is an intention-to-treat analysis with the modification that subjects who are randomized but who do not have the study plasma infusion started will be excluded. Most subjects that do not receive plasma withdraw from the study early (Day 0-2 based in IRC002 data). Therefore, use of the modified intention-to-treat population is thought reasonable for this study. Supplementary intention-to-treat analyses including all randomized subjects for mortality, primary endpoint, and main secondary endpoints will be provided in the final analysis, though there may be limited follow-up data on many of the subjects who did not receive plasma.

12.2 Sample Size and Power Considerations

The planned sample size for the trial is 150 subjects, randomized in an approximately 2:1 ratio to high-titer versus low-titer anti-influenza plasma. To evaluate the power of the study, the following assumptions were made:

- a. The primary analysis will compare the high-titer and low-titer plasmas using a proportional odds model and a two-sided Type I error rate of 0.05.
- b. It is anticipated that very few of these subjects will be randomized and not start study plasma infusion (and so be excluded from the primary analysis) or be lost to follow-up prior to Day 7 (and so have missing data for the primary endpoint). In addition, power is reduced slightly and hence the effective sample size is reduced by interim analyses reviewed by the DSMB. Conservatively, a 10% reduction in the total sample size from 150 to 135 subjects was made to allow for these issues.
- c. Data from the control arm of IRC002 for adults with influenza A infection, NEW score ≥ 3 , and duration of time from onset of symptoms of influenza to randomization ≤ 6 days, suggests the distribution of subjects in the low-titer arm for the primary endpoint shown in the following table:

Table 12: Anticipated Distribution of Subjects in the Ordinal Scale

| | Low-Titer Arm | High-Titer Arm | |
|---|----------------------|-----------------------|-----------|
| | (Based on IRC 002) | 80% Power | 90% Power |
| Died | 10% | 4.3% | 3.7% |
| In ICU | 35% | 20.4% | 18.4% |
| Non-ICU hospitalization, requiring supplemental oxygen | 25% | 23.6% | 22.6% |
| Non-ICU hospitalization, not requiring supplemental oxygen | 10% | 13.3% | 13.4% |
| Not hospitalized, but unable to resume normal activities | 5% | 7.9% | 8.2% |
| Not hospitalized, but with full resumption of normal activities | 15% | 30.6% | 33.7% |
| Proportional odds ratio comparing high titer to low titer | | 2.50 | 2.88 |

Based on the above assumptions, the table also shows the type of true difference (assuming proportional odds) that would be detected with 80% or 90% power. For example, the study would have 80% power to detect a proportional odds ratio of 2.50. This is the odds ratio that arises when comparing the proportion not hospitalized and able to resume normal activities in the high-titer arm (30.6%) to that in the low-titer arm (15%). The proportional odds model assumes that the same odds ratio applies to the cumulative proportions moving up the ordinal scale: for example, for the proportion not hospitalized in the high-titer arm ($30.6+7.9=38.5\%$) to that in the low-titer arm ($15+5=20\%$); or for the proportion alive and not in an ICU in the high-titer arm ($30.6+7.9+13.3+23.6=75.4\%$) to that in the low-titer arm ($15+5+10+25=55\%$).

12.3 Statistical Analysis

A detailed statistical analysis plan will be developed before undertaking any comparative analyses of outcomes for the randomized high and low plasma titers. The following provides a brief summary of approach to analysis for the primary endpoint.

As noted above, the primary analysis will use a modified intention-to-treat approach which excludes randomized subjects who do not have an infusion of study plasma started. Statistical inferences will use a two-sided Type 1 error rate of 0.05, and corresponding 95% confidence intervals.

Analysis of the primary endpoint (ordinal outcome of clinical status at Day 7) will use a proportional odds model with an indicator variable for randomized treatment. It is useful to note that the score test of the treatment effect from a proportional odds model is equivalent to a Wilcoxon rank sum test even if the proportional odds assumption does not hold. If there are missing data for the primary endpoint, then sensitivity analyses will be undertaken to evaluate the sensitivity of study conclusions to the handling of the missing data. The proportional odds model will be extended to undertake comparisons of randomized treatments adjusted for variables that might be predictive of the outcome, for example, the ordinal clinical status at baseline. The model will also be extended to evaluate possible differences in the comparison of randomized treatments between subgroups of subjects (treatment by subgroup interaction), including subgroups defined by sex, age (adult/child), race/ethnicity, ordinal clinical status at baseline, NEW score at baseline, and days since onset of influenza symptoms to randomization.

Binary variables such as 28-day mortality, in-hospital mortality, incidence of new ICU admissions, etc., are expected to occur infrequently and will be compared between randomized arms using exact logistic regression. Quantitative variables such as duration of ICU stay and change from baseline in NEW score, etc., are expected to have reasonably skewed distributions and may be subject to censoring (e.g., for subjects in an ICU on Day 28); these will be compared between randomized arms using non-parametric tests (e.g., Wilcoxon's Test adapted, if necessary, to handle censoring).

Analysis of AE data will primarily be descriptive based on MedDRA coding of events. The proportion of subjects experiencing an SAE and the proportion experiencing a Grade 3 or higher AE will be compared between randomized arms using Fisher's Exact Test.

Analysis of HAI titers will also primarily be descriptive, comparing the geometric mean titers at Days 0, 3, and 7 between randomized arms, to confirm (or otherwise) a difference in titers for subjects receiving high-titer versus low-titer anti-influenza plasma.

For enrolled subjects who were not randomized (i.e. screen failures) or who were randomized but did not receive plasma, the final analysis will detail safety (deaths and SAEs), and reasons they were not randomized or did not receive plasma respectively.

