2.2 Secondary Objectives

1. Evaluate the efficacy and safety of treatment with high-titer versus low-titer anti-influenza immune plasma as an addition to standard care, using the following parameters:

- The ordinal primary outcome assessed at Days 1, 2, 3, 14, and 28
- Duration of initial hospitalization
- 28-day mortality
- In-hospital mortality during initial hospitalization
- Composite of mortality and hospitalization at Days 7, 14, and 28
- Change from baseline to Day 3 and Day 7 in NEW/PEW score
- Duration of supplemental oxygen use among those requiring oxygen at randomization
- Incidence of new oxygen use during the study
- Duration of ICU stay among those requiring ICU admission at randomization
- Incidence of new ICU admission during the study
- Duration of mechanical ventilation use among those requiring mechanical ventilation at randomization
- Incidence of new mechanical ventilation use during the study
- Duration and severity of ARDS among those meeting the definition of ARDS at randomization
- Incidence and severity of new ARDS during the study
- Duration of ECMO use among those requiring ECMO at randomization
- Incidence of new ECMO use during the study
- Change from baseline to Day 3 and Day 7 SOFA score for age \geq 18 years, and PELOD score for age $<$ 18 years
- Disposition (home, rehabilitation, chronic nursing facility, initial hospitalization ongoing at 28 days, died in hospital) following the initial hospitalization

- Percent of subjects with influenza virus detectable in OP sample at Day 3

2. Compare the plasma and control groups for HAI titers at Days 1, 3, and 7.

3. Evaluate the safety of high titer anti-influenza plasma as compared to low titer plasma as assessed by:

- Cumulative incidence of grade 3 and grade 4 adverse events (AEs)
- Cumulative incidence of serious adverse events (SAEs)

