5.9 Study Plasma Administration

Study plasma should be administered as soon as possible. The plasma should be started no later than 12 hours after randomization for units that are available at a site, and no later than 24 hours for units that are shipped from the repository for that subject. The plasma infusion rate will be determined by the individual sites based on institutional policy.

Before administration of study plasma, the investigator (or designated study staff) must verify the plasma label(s) to confirm that the DIN(s) on the plasma unit(s) match the IWRS randomization notification email for the subject, as well as to confirm the appropriate dose to be administered (refer to Section 5.7). Plasma DIN(s) and plasma product code(s) should be recorded in source documents at the time of infusion along with the volume administered.

The calendar date and 24-hour clock time for study plasma administration should be recorded for the start and end of each infusion. The intervals between units may occur per a site's blood establishment SOPs and/or normal practice. Pretreatment to minimize transfusion reactions (e.g. acetaminophen, diphenhydramine, etc.) according to local institutional policies are permitted in this study, but any such medications should be captured as concomitant medications.

If an AE develops during infusion, the infusion may be slowed temporarily or permanently discontinued, as deemed appropriate by the investigator. As a guide, local side effects (e.g., infusion site burning) or non-allergic systemic effects (e.g., chills) can generally be alleviated by slowing the rate of infusion, whereas allergic side effects (e.g., rash, wheezing, hypotension) should result in the cessation of study plasma infusion. All grade 3 or grade 4 AEs, and all SAEs occurring during study plasma administration should be captured as noted in Section 10.2. Additionally, any AEs resulting in plasma discontinuation (regardless of AE grade) should be recorded.

The investigator is ultimately responsible for making the decision to slow or stop study plasma infusion. If the infusion is discontinued, the subject should be treated according to best available local practices and procedures, and the Medical Monitor should be notified. Reason(s) for premature discontinuation of any plasma infusion must be documented in the medical record (source document) and on the eCRF.

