6.3.4 Study Plasma Administration

After all baseline evaluations and randomization have been completed, subjects will receive the study plasma. Refer to Section [5.7](#) for dosing information. The calendar date and 24-hour clock time for study plasma administration should be recorded for the start and end of each infusion.

Vital signs should be obtained during plasma infusion according to institutional policies. Vital signs during infusion are not collected in the database. All grade 3 or grade 4 AEs (e.g. hypotension) or other events (chest pain, rash, etc.) and all SAEs occurring during study plasma administration should be captured as noted in Section [10.2](#).

6.3.5 Study Day 1

Day 1 is always the calendar day following the day of randomization, even if the plasma infusion starts late in the day of randomization or if the plasma infusion starts on the calendar day following the day of randomization. However, plasma administration should be completed prior to collecting the Day 1 visit procedures.

6.3.5.1 Clinical Data on Day 1

- Vital signs, including SpO₂. These values may be obtained from clinically collected information if they were obtained within 4 hours of the study assessment. Vital signs must be collected in a complete set within 30 minutes of each other.
- Clinical data
 - Assessment of clinical status (6-point ordinal scale)
 - Glasgow coma scale
 - Organ dysfunction score
 - SOFA score for age \geq 18 years
 - PELOD score for age $<$ 18 years
 - Measures of clinical support:
 - Hospitalization
 - Oxygen requirement
 - Mechanical ventilator requirement
 - ICU requirement
 - ECMO requirement
 - Chest x-ray finding if performed for clinical indication
 - Assessment of ARDS using PaO₂ (or SpO₂), FiO₂, and recent chest x-ray data.
- Review new medical conditions, concomitant medication, and evaluate for AEs

6.3.5.2 Clinical Laboratory Tests on Day 1

The following laboratory test will be performed:

- CBC with differential white cell count (to include neutrophil and lymphocyte percentages), hemoglobin, hematocrit, and platelets
- Blood chemistries (creatinine, glucose, total protein, ALT/GPT, AST/GOT, total bilirubin)
- PT/INR

Results from laboratory tests performed for clinical indications $<$ 12 hours before the visit may be used if available. Any tests not collected clinically, should be obtained according to the protocol.

6.3.5.3 Research Procedures on Day 1

The following research procedures will be performed:

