## **1. General analysis considerations**

Unless otherwise specified, data summaries and analyses will be presented overall and by randomized arm. For tables with categorical variables, the number (%) will be presented. For tables with continuous variables, the mean, standard deviation, median, 25th and 75th percentiles, min and max will be presented. The number with missing values will also be shown. In calculation of percentages, subjects with missing data will not be included in the denominator.

Unless otherwise stated, analyses will be restricted to subjects with non-missing data or available follow-up time for the endpoint of interest. Tables/figures will show the number of subjects included in the analysis. Sensitivity analyses may be undertaken using (1) the last available measurement carried forward, and (2) extreme scenarios in which subjects are assigned in the worst status in one randomized arm and the best in the other (and vice versa) to illustrate the sensitivity of conclusions to any incompleteness in the data.

Appendices to the report will provide tables and figures for adults (age  $\geq 18$  years) and children (age  $< 18$  years) separately.

To help protect participant confidentiality, listings of individual patient level data will be minimized as much as possible. Dates will also not be presented in listings; instead, for example, listings will present details as days since randomization.

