### **9. Pharmacokinetic analysis**

- a. Figure and associated table for each strain tested: geometric mean HAI titer with 95% CI on study Days 0, 1, 3 and 7.

- b. Figure and associated table for HAI from infecting strain (H1 or H3): geometric mean HAI titer with 95% CI on study Days 0, 1, 3 and 7.  
*(note – this is the PK from the plasma as well as the natural development of antibodies occurring after an infection)*
- c. Figure and associated table for HAI from non-infecting strain (H1 or H3): geometric mean HAI titer with 95% CI on study Days 0, 1, 3 and 7. *(note – this is the PK from the plasma and should not be significantly affected from development of antibodies to a different strain)*
- d. Figure and associated table for each strain tested: geometric mean HAI titer ratio (versus Day 0 titer) with 95% CI on Days 1, 3 and 7.
- e. Figure and associated table from infecting strain (H1 or H3): geometric mean HAI titer ratio (versus Day 0 titer) with 95% CI on Days 1, 3 and 7.
- f. Figure and associated table from non-infecting strain (H1 or H3): geometric mean HAI titer ratio (versus Day 0 titer) with 95% CI on Days 1, 3 and 7.

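### SAP section 9 shows HAI titres by arm but gives no estimate of the difference between arms, which secondary objective 2 asks for

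*Protocol*

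**What the plan says.** - Protocol 2.2, objective 2: "Compare the plasma and control groups for HAI titers at Days 1, 3, and 7".
- Protocol 12.3: "Analysis of HAI titers will also primarily be descriptive". The same sentence goes on to "comparing the geometric mean titers at Days 0, 3, and 7 between randomized arms", with the aim of confirming or refuting a difference. Day 1 is not in that list of days.
- SAP 9, items a to c: "geometric mean HAI titer with 95% CI on study Days 0, 1, 3 and 7", for each strain, the infecting strain and the non-infecting strain. Items d to f, for the same three groupings: "geometric mean HAI titer ratio (versus Day 0 titer) with 95% CI on Days 1, 3 and 7".
- SAP 1, as the default for every output: "data summaries and analyses will be presented overall and by randomized arm".
- SAP 10.2 to 10.6 specify an odds ratio or a difference between treatments, with CI and p-value, for clinical status, the composite, disposition, durations, incident support, severity scores and viral detection. SAP 9 has no counterpart.
- On Day 1 timing, protocol 6.3.5 fixes Day 1 as the calendar day after randomization and says "plasma administration should be completed prior to collecting the Day 1 visit procedures". Protocol 5.9 allows the infusion to start up to 12 hours after randomization for on-site units and "no later than 24 hours for units that are shipped from the repository for that subject". The analysis window for Day 1 in SAP Table 1 is Day 1 alone.

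**The concern.** Protocol 1.3.1 justifies low-titer plasma as the control because it tests whether HAI-detectable antibody is the active component of plasma. If the primary result is null, readers will ask how far recipients' titres separated. That calls for an estimate of the separation and its uncertainty, and SAP 9 does not define one. Readers would have to compare two by-arm intervals by eye, or analysts would have to choose a contrast after seeing the data. Day 0 titre enters only as the denominator of a ratio, which generally uses baseline less efficiently than a covariate does.

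A smaller issue concerns Day 1, the sample closest to the infusion. Under the permitted start times some Day 1 samples could precede the end of the infusion, which would pull the Day 1 contrast towards no difference. SAP 9 has no rule for such samples.

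**Working it through.** **Inputs from the documents.** Protocol 12.2 gives an effective sample of 135 at about 2:1, taken here as 90 v 45. It is the sample behind the stated power. With the Whitehead formula, power = Φ(ln OR × √[N × (2/9) × (1 − Σp̄³)/3] − 1.96), N = 135 gives 80.7% at OR 2.50 and 90.3% at OR 2.88, against the stated 80% and 90%. The documents give no power or precision figure for HAI, so there is none to reproduce.

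The A/H1N1 geometric mean titres from IRC002 appear twice and differ, with no explanation:

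| Source | Plasma, Day 0 → Day 2 | Standard care, Day 0 → Day 2 | Day 2 ratio | Ratio of Day 0 ratios |
|---|---|---|---|---|
| Protocol 1.2.2.4 | 29 → 63 | 32 → 40 | 63/40 = 1.58 | (63/29)/(40/32) = 1.74 |
| Protocol 5.3 | 26 → 63 | 30 → 36 | 63/36 = 1.75 | (63/26)/(36/30) = 2.02 |

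**Assumed inputs.** Neither the SD of log titre nor its correlation r with Day 0 is given for influenza A. Protocol Table 4 (influenza B, 2 to 4 subjects per cell) allows a rough back-calculation: SD = ln(upper limit/mean) × √n / t. This gives 0.4 to 2.2 on the natural-log scale, pooled about 1.3. I use SD 1.2 with a range of 0.7 to 1.8, and r from 0.3 to 0.7, with equal SDs at Day 0 and follow-up.

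**Step 1: two by-arm intervals against one direct interval.** Non-overlap of two 95% CIs needs a log difference above 1.96 × SD × (1/√90 + 1/√45). A direct 95% CI needs 1.96 × SD × √(1/90 + 1/45).

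- Ratio of the two: (0.1054 + 0.1491)/0.1826 = 1.39. This does not depend on the SD.
- At SD 1.2 and a true ratio of 1.74: ln 1.74 = 0.554, standard error = 1.2 × 0.1826 = 0.219, z = 2.53.
- Chance that a direct post-only CI excludes 1: Φ(2.53 − 1.96) = 71.5%.
- Chance that the two by-arm CIs separate: Φ(2.53 − 1.39 × 1.96) = about 42%.
- At SD 0.7 the same pair is 99% and 95%. At SD 1.8 it is 39% and 15%.

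**Step 2: use of Day 0.** The variance of the between-arm log contrast, relative to post-only, is 2(1 − r) for a contrast of Day 0 ratios and 1 − r² with Day 0 as covariate. On the log scale, CI width with the covariate is therefore √[(1 + r)/2] of the Day 0 ratio contrast and √(1 − r²) of the post-only contrast.

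| r | Narrower than Day 0 ratio contrast | Narrower than post-only | Power at ratio 1.74, SD 1.2: post-only / Day 0 ratio / covariate |
|---|---|---|---|
| 0.3 | 19% | 5% | 71.5% / 57% / 75.5% |
| 0.5 | 13% | 13% | 71.5% / 71.5% / 83% |
| 0.7 | 8% | 29% | 71.5% / 90% / 94% |

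At SD 0.7 every direct contrast has at least 95% power at a ratio of 1.74. At SD 1.8, post-only has 39% and the covariate model 42% to 66%.

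**Step 3: Day 1 timing.** Take a subject randomized at 20:00 on Day 0 whose units are shipped. Protocol 5.9 allows a start as late as 20:00 on Day 1. That leaves at most four hours of the Day 1 window for the infusion and any later sample. On-site units (12-hour limit) can also start on the Day 1 calendar date after a late randomization. So the three statements can conflict, but only for late or shipped infusions. The documents give no frequency, so no size is attached.

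**The case against.** The strongest reply is that protocol 12.3 calls the HAI analysis primarily descriptive and SAP 9 delivers that. Titres and fold changes appear by arm with CIs on every objective day. Because the arms are independent, a reader could combine the two intervals into a between-arm ratio. Unit titres are fixed by design (at least 1:80 v 1:10 or less), and SAP 7.2 tabulates the titres infused and lists units given outside the assignment, so HAI in recipients is not the only evidence that the treatments differed.

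Much of that stands, and it rules out several stronger readings:

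- A reader might infer that objective 2 goes unanswered. It does not; it is answered by arm, without a contrast.
- A reader might infer that baseline titre is ignored. Items d to f of SAP 9 use it as a ratio; only the covariate use is missing.
- A reader might infer from protocol 12.3 that Day 1 is dropped. SAP 9 includes it, as do objective 2, protocol 7.1 and protocol 12.4.2, so that omission is a wording slip.
- A reader might take the 29% narrowing at r = 0.7 as the gain over the SAP. It is the gain over a post-only contrast; against the SAP's own ratio the gain at that r is 8%.
- A reader might infer that many Day 1 samples precede infusion. Nothing supports a share, the 8AM timing belongs to the clinical scales rather than the blood draws, and protocol 6.3.5 says infusion should come first.

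What the reply does not remove is that the sentence calling the analysis descriptive also promises a comparison of the arms. A ratio with a CI fits a descriptive analysis, and readers should not have to construct it.

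**Conclusion.** The point holds in a limited form. SAP 9 does not carry through the between-arm comparison in objective 2 and protocol 12.3. Judging separation from by-arm intervals needs a log difference about 1.4 times larger than a direct CI requires; this follows from 90 v 45 and a common SD. Covariate adjustment narrows the interval by a further 8% to 19% against a contrast of Day 0 ratios, or 5% to 29% against post-only. These gains rest on assumed correlations of 0.3 to 0.7, and the power figures also on assumed SDs. With a small SD all direct contrasts perform well. The Day 1 conflict is real for late or shipped infusions and of unknown frequency. HAI is a secondary, PK-type measure, so the primary analysis and its power are untouched.

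**What to change.** - **SAP 9, main change.** For Days 1, 3 and 7, add the between-arm geometric mean titre ratio with 95% CI from a linear model on log HAI with randomized arm and Day 0 log HAI as terms. Report it by strain and for the infecting and non-infecting subtypes, beside the existing by-arm displays.
- **SAP 9, Day 1.** Keep all mITT subjects with a Day 1 titre in the main model, because dropping those infused late would select on an event after randomization. Where draw times are available, add a sensitivity analysis for samples taken before the infusion ended.
- **Protocol 5.9 and 6.3.5.** Reconcile the permitted start times, in particular the 24-hour limit for shipped units, with the statement that plasma should be completed before Day 1 procedures. Which of them should change is not a statistical question.
- **Protocol 12.3.** Align the listed days with objective 2, as a wording correction only.

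The cost is a few lines of SAP text and one model per day and titre grouping. The main contrast needs no new data. The sensitivity analysis needs clock times for the Day 1 draws; infusion start and end times are recorded under protocol 5.9, but the documents do not say that research draw times are.
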